Because the **primary barrier to CM implementation is related to cost**, we will conduct a cost-benefit and cost-effectiveness analysis to assess the relative economic viability of each CM intervention. [Finally, little is known about moderators of outcomes in CM because past studies focused on moderators in isolation, without a theoretical model. We will use the NIAAA Addictions Neuroclinical Assessment (ANA) framework to determine how its 3 domains – **executive functioning, negative emotionality, and alcohol-related incentive salience – predict treatment outcomes across CM adaptations.**] This study promises to have a high impact because it will determine if CM adaptations can improve outcomes and reduce costs, and identify moderators of CM efficacy in a high-cost, complex, and understudied population. Our **Specific Aims** are to:

1. Determine whether levels of alcohol abstinence during the last 3 months of treatment and a 6-month follow-up period vary by CM condition. *We hypothesize that participants in the 2 modified CM conditions will attain higher rates of abstinence than those in the Usual CM condition.*
2. Determine whether randomization groups differ on secondary alcohol outcomes, drug use, psychiatric severity, HIV risk behavior, and cigarette smoking. *We hypothesize that participants in the 2 modified CM conditions will attain better outcomes than those in the Usual CM condition.*
3. Conduct cost-benefit and cost-effectiveness analyses to determine the relative economic viability of the 3 CM conditions. *We hypothesize that the 2 modified CM conditions will dominate the Usual CM group, and the Shaping CM condition will be the most cost-effective.*
4. [Identify ANA-based moderators of CM treatment response across the sample and within CM conditions. *We hypothesize that higher executive dysfunction, negative emotionality, and alcohol-related incentive salience will be associated with lower levels of alcohol abstinence across all CM conditions. We also hypothesize that participants with higher levels of these characteristics will be more likely to respond to the modified CM conditions than to the Usual CM condition.*]

**Table 1.** Mean number of consecutive alcohol-negative samples

	CM M (SD)	Control M (SD)
EtG < 500 ng/mL	11.6 (10.7)	4.9 (3.5)
EtG > 499 ng/mL	4.6 (6.9)	3.7 (7.3)

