## F. Data Collection and Measures

**4.F.1 Schedule.** Data collection will occur during the study period (weeks 1-20, including baseline assessment, induction, and treatment) and the follow-up period (weeks 21-47) as shown in **Table 4**. Baseline data collection will take ~120 minutes and include urine tests, self-reported data, and cognitive tests. Participants will provide urine samples every Monday, Wednesday, and Friday during the study period. At each visit, they will complete brief self-report questionnaires on alcohol use. Weeks 4, 8, 12, 16, and 20 will include 45-minute data collection visits to assess other outcomes. During follow-up, participants will be scheduled for 45-minute visits at weeks 25, 33, and 47. They will receive a \$30 gift card for completing the baseline interview and a \$20 gift card for completing each interview in weeks 4, 8, 12, 16, 20, 25, 33, and 47.

**Table 4.** Data collection schedule

Measure	Baseline Wk 0	Induction Wk 1-4	Treatment Wk 5-20	Follow-up Wk 25, 33, 47
Eligibility Criteria				
DSM-5 inclusion/exclusion diagnosis (interview)	✓			
Consumer at participating agency (self-report)	✓			
Age (self-report)	✓			
Current heavy drinking (self-report)	✓			
Health and risk factor exclusions (self-report/observation)	✓			
Primary Outcome				
Alcohol use (ethyl glucuronide)	✓	3x / Wk	3x / Wk	Every visit
Other Secondary Outcomes				
Any/Heavy drinking: ATLFB (self-report)	✓	3x / Wk	3x / Wk	Every visit
Recent heavy drinking (ethyl glucuronide)	✓	3x / Wk	3x / Wk	Every visit
Alcohol cravings (self-report)	✓	Weekly	Weekly	Every visit
Alcohol/ drug severity: ASI-Lite (self-report)	✓	Wk 4	Wk 8,12, 16, 20	Every visit
Drug use (biochemical)	✓	3x / Wk	3x / Wk	Every visit
Cigarette Timeline FollowBack (self-report)	✓	Wk 4	Wk 8,12, 16, 20	Every visit
Nicotine dependence: Fagerstrom (self-report)	✓	Wk 4	Wk 8,12, 16, 20	Every visit
HIV risk behavior (self-report)	✓	Wk 4	Wk 8,12, 16, 20	Every visit
Psychiatric symptoms: PANSS (interviewer rating)	✓	Wk 4	Wk 8,12, 16, 20	Every visit
Economic Measures				
Drug Abuse Treatment Cost Analysis Program tool				Wk 47
Healthcare use by patient medical records	Past 12 mo	Throughout	Throughout	Throughout
Non-Study Resources Form (self-report)	✓	Wk 4	Wk 8,12, 16, 20	Every visit
Quality-Adjusted Life-Years: EQ-5D (self-report)	✓	Wk 4	Wk 8,12, 16, 20	Every visit
ANA Moderators				
Negative emotionality: NIH Toolbox (self-report)	✓	Weekly		

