Executive functioning: NIH Toolbox/MCQ (cognitive tests/self-report)	✓			
Alcohol incentive salience (self-report/cognitive tests)	✓			
Adverse Events				
Alcohol withdrawal: SHOT (interviewer rating)	✓	3x / Wk	3x / Wk	Every visit
Participant safety (self-report/observation)	✓	3x / Wk	3x / Wk	Every visit

**4.F.2 Measures Overview.** Baseline data will include assessment of eligibility criteria and measures for Aims 1-4. Our primary outcome (Aim 1) is biochemically confirmed alcohol abstinence, measured 3 times per week during the final 12 weeks of the treatment period (weeks 9-20) and 3 times total during the 6-month follow-up period. Aim 2 outcomes will be collected in a similar fashion. Cost data will be collected for 12 months before and after randomization. Aim 3 outcomes consist primarily of self-reported use of non-study

healthcare resources, QALYs, days of alcohol abstinence, and heavy drinking days averted. We will collect data on each ANA domain to test for predictors of alcohol abstinence during CM interventions.

**4.F.3 Eligibility Criteria.** Age and frequency of recent drinking will be assessed by phone screening. The Structured Clinical Interview for DSM-5 (SCID-5) interview, clinical trials version, will be administered to assess diagnostic inclusion (SMI, AUDs) and exclusion criteria. Competency to provide informed consent will be assessed as described in Section 4.C.2.

**4.F.4 Primary Outcome.** Our primary outcome will be alcohol abstinence during the last 3 months of treatment and the 6-month follow-up period. At each study visit, urine samples will be collected and analyzed onsite for EtG by using the [commercially available Diagnostic Reagents Incorporated EtG immunoassay on an Indiko Bench Top Analyzer (ThermoFischer Scientific, Freemont, CA).] We will use the assay to create a binary indicator of alcohol use defined by EtG < 100 ng/mL. That threshold was used in our first funding period and in our ongoing CM trials. While it is not associated with false positives due to non-beverage alcohol exposure, we will ask participants to abstain from using all alcohol-containing products, like hand sanitizer.

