## **G. Data Analysis**

**4.G.1 General Data Analytic Strategy.** We will analyze outcome data in a manner consistent with previous RCTs of CM. We will analyze our primary and secondary outcomes longitudinally across the final 12-weeks of CM (when all reinforcers are contingent on alcohol abstinence) and the 6 month follow-up period to estimate the effects of CM. Below we discuss our strategy for the primary outcome of alcohol use, which is very similar to our strategy for Aim 2 outcomes. We will compute means and standard deviations for continuous variables and percentages and frequencies for categorical variables. Measures that fail to satisfy the assumptions of parametric tests will be transformed to adjust for differences in variability or skewness. Alternatively, nonparametric tests may be used. Our alpha threshold for statistical significance will be 0.05.

**4.G.2 Specific Data Analytic Techniques.** Groups will be compared for differences in demographics and pre-treatment drug and alcohol use, including data collected during the baseline interview and the 4-week induction period. We will **evaluate sex as a biological variable** by investigating whether sex moderates treatment outcomes. Comparisons will use analysis of variance (ANOVA) for continuous variables and chi-square tests for categorical variables (with Bonferroni-adjusted follow-up tests if necessary). Variables that differ between groups at baseline and during the induction period will be used as covariates in subsequent analyses, as will baseline measures that co-vary with the outcome measures.

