**Aims 1 and 2.** Recent alcohol use will be documented by using urine test results (binary outcome: EtG < 100 ng/mL or EtG > 100 ng/mL) and analyzed by using generalized estimating equations (GEE), generalized regression, and Cox proportional hazard regression techniques. Other outcome measures will be derived from recent alcohol use, such as 1) alcohol use (yes/no) over time; 2) longest duration of abstinence; 3) total number of periods of alcohol abstinence; 4) time to first alcohol abstinence; and 5) time to relapse after a specified period of alcohol abstinence. These outcomes will be examined across CM condition, time, and the CM condition-by-time interaction to determine whether one condition is superior to the others in promoting discontinuation of alcohol use. Additional analyses will be conducted by defining alcohol use in various clinically descriptive ways, such as the mean number of heavy drinking days or heavy drinking months across groups. Group comparisons of other Aim 2 outcomes will be assessed and evaluated in a similar fashion (e.g., longest duration of drug abstinence, mean HIV risk score).

Analyses will be conducted on the intent-to-treat sample (n=240). This is a conservative approach aimed at avoiding overestimation of the treatment effect. It includes all participants who were randomly assigned to treatment conditions, regardless of treatment completion. GEE models will be used to evaluate the differential change in primary and secondary outcomes by study condition over the 12-month study period (1 month before the baseline interview plus the 1-month induction, 4-month treatment, and 6-month follow-up periods), and whether condition interacts with change over time. This approach allows us to characterize between-group differences in longitudinal outcomes. We hypothesize that the modified interventions (High-Magnitude CM and Shaping CM) will lead to higher rates of alcohol abstinence than the Usual CM intervention. If the condition-by-time interaction variable is significant, we will conduct planned comparisons to examine the hypothesized pattern for each outcome. Such an approach will allow us to test this set of hypotheses with specificity. We will also conduct a direct comparison of the High-Magnitude CM group and the Shaping CM group.

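### Aim 1 covers weeks 9-20 and follow-up as one outcome, with no contrast pre-specified for either phase, so an averaged condition effect does not by itself support a follow-up claim

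*Combined protocol and SAP*

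**What the plan says.** Aim 1 (Section 1) reads: "Determine whether levels of alcohol abstinence during the last 3 months of treatment and a 6-month follow-up period vary by CM condition". The hypothesis attached to it, higher abstinence in the two modified conditions than in Usual CM, does not distinguish the two periods.

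Section 4.F.2 sets three EtG samples a week over the last 12 treatment weeks (weeks 9-20) and "3 times total during the 6-month follow-up period". Section 4.F.1 fixes the timing: "participants will be scheduled for 45-minute visits at weeks 25, 33, and 47".

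Section 4.G.1 says outcomes will be analysed "longitudinally across the final 12-weeks of CM (when all reinforcers are contingent on alcohol abstinence) and the 6 month follow-up period". Section 4.G.2 says the binary EtG result will be "analyzed by using generalized estimating equations (GEE), generalized regression, and Cox proportional hazard regression techniques", and adds: "These outcomes will be examined across CM condition, time, and the CM condition-by-time interaction". Planned comparisons follow if the condition-by-time interaction is significant. A direct comparison of High-Magnitude with Shaping CM is also announced, with no phase attached.

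The same section describes a GEE over 12 months, starting a month before baseline and including induction. That is wider than the window in 4.F.2 and 4.G.1. The coding of time, the working correlation and the conclusion to be drawn if the interaction is not significant are not stated.

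**The concern.** Whether incentives raise abstinence while they are on offer, and whether abstinence outlasts them, are different questions. The plan promises an answer to both: Section 4.B schedules follow-up visits to assess long-term outcomes, and Section 3 counts follow-up beyond 3 months among the study's innovations. One phase supplies 36 samples per person and the other 3.

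If the result is summarised as one condition effect over both periods, a benefit that ends with the prizes could be described as higher abstinence during treatment and follow-up, and a benefit seen only after treatment would be heavily diluted.

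The gate adds a second problem. Over weeks 9-20 plus follow-up, a steady and durable benefit is a condition effect without an interaction, so it would not be expected to trigger the planned comparisons. Over the 12-month window, a significant interaction might reflect only the change from induction to treatment and need say nothing about follow-up.

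**Working it through.** **1. Sample counts (4.F.1, 4.F.2).** On treatment: 3 x 12 = 36. Follow-up: 3. On-treatment share: 36/39 = 92.3%. In the 12-month window, Table 4 gives 1 baseline + 12 induction + 48 treatment + 3 follow-up = 64 samples, so follow-up is 3/64 = 4.7%.

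**2. Weight in an averaged condition effect.** With working correlation matrix R, the visit weights are proportional to R⁻¹1. R is not stated, so several forms were tried, all with complete data:

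| Working correlation | Weight on weeks 9-20 |
|---|---|
| Independence or exchangeable | 92% |
| AR(1) by visit, 0.5 to 0.9 | 90% to 79% |
| Decay in calendar time, weekly correlation 0.5 to 0.95 | about 43% to 63% |

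At 92%, a 10-point effect on treatment with none afterwards averages 10 x 36/39 = 9.2 points; the reverse pattern averages 10 x 3/39 = 0.8. At 43-63%, the first pattern still averages 4.3-6.3 points.

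**3. Would a linear time term repair this?** This is an illustration on the probability scale, with independence and Monday/Wednesday/Friday visits placed at w, w + 2/7 and w + 4/7. Let the true difference be 10 points at the 36 treatment visits and 0 at the 3 follow-up visits.
- Mean week 16.34; sum of squares for time 1,810.5.
- Slope = -10 x (25 + 33 + 47 - 3 x 16.34)/1,810.5 = -559.8/1,810.5 = -0.309 per week.
- Intercept = 9.23 + 0.309 x 16.34 = 14.28.
- Fitted difference: week 25, 14.28 - 7.73 = 6.6; week 33, 14.28 - 10.20 = 4.1; week 47, 14.28 - 14.52 = -0.2.

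The line is about right at week 47 but shows a benefit at weeks 25 and 33 where there is none.

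**4. Power.** Section 4.G.3 states at least 85% power for a 7-point difference with 60 per group. The base rate, within-person correlation and number of repeats are not given, so the figure cannot be reproduced. With 39 equally weighted samples and an assumed base rate of 10-50%, it is reached at a within-person correlation of about 0.04-0.12. It is therefore not shown to be wrong.

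For follow-up alone (two-sided 0.05 assumed, 60 per arm, all three visits attended):

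SE = sqrt[p(1-p) x (1 + 2ρ)/3 x 2/60]; detectable difference at 80% power = 2.80 x SE.

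| Base rate p | ρ | SE (points) | Detectable difference (points) |
|---|---|---|---|
| 10% | 0 | 3.2 | 9 |
| 30% | 0.3 | 6.1 | 17 |
| 30% | 0.7 | 7.5 | 21 |
| 50% | 0.7 | 8.2 | 23 |

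A two-proportion calculation that lets the second arm's rate move with the effect gives about 11-22 points over the same range. For a 7-point difference, the most favourable corner of the table gives z = 7/3.16 - 1.96 = 0.25, or 60% power (49% by the two-proportion method). No setting with a base rate of 10-50% reaches 85%, even at zero correlation.

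**The case against.** A reader might infer that the plan pools 39 samples into one proportion, that it therefore cannot support any conclusion about follow-up, and that a follow-up effect would be invisible. The documents do not support that. Section 4.G.1 calls the analysis longitudinal, and 4.G.2 includes time and condition-by-time. A benefit that ends with the prizes, or begins only after them, is an interaction. Under the linear coding above, the three follow-up visits carry 1,292.5/1,810.5 = 71% of the information on time, so they are far from ignored. A follow-up estimate could be drawn from the planned model.

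Nor is 92% a fixed analysis weight, as step 2 shows. The detectable differences rest on assumed inputs, and 4.G.3 never claims 7 points for follow-up alone.

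The team also has a record of reporting by phase: Section 2.B.6 gives treatment and follow-up results separately for drinking days, heavy drinking and stimulant use. And 4.G.3 mentions planned comparisons after an omnibus test, which could be read as a test of the condition effect.

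All this limits the wording but does not remove the point. A model that could yield a follow-up contrast is not a commitment to one, and the only trigger named in 4.G.2 is the interaction. The simplest time coding misstates the effect at two of the three follow-up visits. The pilot intervals also show how imprecise follow-up can be: for heavy drinking, 2.3-5.2 in treatment against 1.8-13.5 in follow-up, about 2.5 times wider on the log scale (ln 7.5/ln 2.26).

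**Conclusion.** The point stands as a gap in pre-specification, with a better method available from data already planned. No on-treatment or follow-up contrast is defined, and the comparisons that might supply one depend on a test that a constant benefit over weeks 9-20 and follow-up would not be expected to pass. A single averaged effect is mostly an on-treatment effect: 92% under independence or exchangeable correlation with complete data, and about 43-90% under the other structures tried. As specified, it does not by itself support a statement about follow-up.

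For follow-up alone the detectable difference is about 9-23 points, assuming 60 per arm with all three samples, a base rate of 10-50% and within-person correlation of 0-0.7. The stated 85% power for 7 points should not be carried over to that phase. It does not follow that the stated power is wrong for the combined outcome, or that the planned GEE is unsuitable.

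**What to change.** In 4.G.2, keep the GEE and make these changes:
- Code time with a phase factor (weeks 9-20 against weeks 25, 33 and 47) and include condition-by-phase. State the working correlation.
- Pre-specify the condition contrasts in each phase, with confidence intervals, to be reported whether or not the interaction is significant.
- State which phase is primary and how multiplicity across contrasts and phases is handled.
- Limit any claim about follow-up to the follow-up contrast.
- Reconcile the 12-month window in 4.G.2 with the window in 4.F.2 and 4.G.1.

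In 4.G.3, give the follow-up detectable difference with its assumed base rate, correlation and number of contributing participants.

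The cost is analysis-plan wording and a small change to the model; no visits, samples or participants are added. The downside is that the follow-up contrast will be imprecise and must be reported as such. A wide interval there is not evidence that the benefit has gone.

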## **G. Data Analysis**

**4.G.1 General Data Analytic Strategy.** We will analyze outcome data in a manner consistent with previous RCTs of CM. We will analyze our primary and secondary outcomes longitudinally across the final 12-weeks of CM (when all reinforcers are contingent on alcohol abstinence) and the 6 month follow-up period to estimate the effects of CM. Below we discuss our strategy for the primary outcome of alcohol use, which is very similar to our strategy for Aim 2 outcomes. We will compute means and standard deviations for continuous variables and percentages and frequencies for categorical variables. Measures that fail to satisfy the assumptions of parametric tests will be transformed to adjust for differences in variability or skewness. Alternatively, nonparametric tests may be used. Our alpha threshold for statistical significance will be 0.05.

**4.G.2 Specific Data Analytic Techniques.** Groups will be compared for differences in demographics and pre-treatment drug and alcohol use, including data collected during the baseline interview and the 4-week induction period. We will **evaluate sex as a biological variable** by investigating whether sex moderates treatment outcomes. Comparisons will use analysis of variance (ANOVA) for continuous variables and chi-square tests for categorical variables (with Bonferroni-adjusted follow-up tests if necessary). Variables that differ between groups at baseline and during the induction period will be used as covariates in subsequent analyses, as will baseline measures that co-vary with the outcome measures.

**Aims 1 and 2.** Recent alcohol use will be documented by using urine test results (binary outcome: EtG < 100 ng/mL or EtG > 100 ng/mL) and analyzed by using generalized estimating equations (GEE), generalized regression, and Cox proportional hazard regression techniques. Other outcome measures will be derived from recent alcohol use, such as 1) alcohol use (yes/no) over time; 2) longest duration of abstinence; 3) total number of periods of alcohol abstinence; 4) time to first alcohol abstinence; and 5) time to relapse after a specified period of alcohol abstinence. These outcomes will be examined across CM condition, time, and the CM condition-by-time interaction to determine whether one condition is superior to the others in promoting discontinuation of alcohol use. Additional analyses will be conducted by defining alcohol use in various clinically descriptive ways, such as the mean number of heavy drinking days or heavy drinking months across groups. Group comparisons of other Aim 2 outcomes will be assessed and evaluated in a similar fashion (e.g., longest duration of drug abstinence, mean HIV risk score).

Analyses will be conducted on the intent-to-treat sample (n=240). This is a conservative approach aimed at avoiding overestimation of the treatment effect. It includes all participants who were randomly assigned to treatment conditions, regardless of treatment completion. GEE models will be used to evaluate the differential change in primary and secondary outcomes by study condition over the 12-month study period (1 month before the baseline interview plus the 1-month induction, 4-month treatment, and 6-month follow-up periods), and whether condition interacts with change over time. This approach allows us to characterize between-group differences in longitudinal outcomes. We hypothesize that the modified interventions (High-Magnitude CM and Shaping CM) will lead to higher rates of alcohol abstinence than the Usual CM intervention. If the condition-by-time interaction variable is significant, we will conduct planned comparisons to examine the hypothesized pattern for each outcome. Such an approach will allow us to test this set of hypotheses with specificity. We will also conduct a direct comparison of the High-Magnitude CM group and the Shaping CM group.

**Aim 3.** We will conduct a systematic economic evaluation of the 3 CM conditions. We will estimate the relative economic value of each intervention by conducting cost-benefit and cost-effectiveness analyses. The economic evaluation will follow the guidelines recommended by the **Panel on Cost Effectiveness in Health and Medicine**, Glick et al. and Drummond. Cost-benefit analyses will entail determining the costs of each condition and extrapolating the downstream savings resulting from reduced alcohol consumption and reduced alcohol-related consequences relative to Usual CM, at which point the estimated net benefit of each condition can be compared. The primary outcome will be the incremental cost-effectiveness ratio (ICER), which will be the incremental cost of one CM condition relative to another, divided by the incremental effectiveness of one CM condition relative to another. The most cost-effective condition will be identified by using the rules of dominance and extended dominance. The primary economic effectiveness outcome in the denominator of each ICER will be the QALY, a measure that incorporates both duration and health-related quality-of-life, and is **recommended as the primary effectiveness outcome measure** for economic evaluation studies by the Panel on Cost Effectiveness in Health and Medicine. In addition to capturing a wider range of consequences than clinical effectiveness measures, QALYs permit comparisons across diseases and interventions, enabling broader economic interpretation. In addition, generally accepted cost-effectiveness thresholds for defining value have been established for QALYs, but not for clinical measures. Nevertheless, **we will also calculate ICERs by using** the clinical effectiveness measures of **duration of alcohol abstinence**, to permit comparisons with existing economic evaluations of CM interventions that relied on measures of abstinence, and **number of heavy drinking days averted** a clinically significant alcohol outcome measure.

Analyses will be conducted from the perspectives of the payer of healthcare services (i.e., the insurer), the treatment provider, and society. The payer and provider represent important perspectives, given the pivotal role played by each in sustaining the intervention, while the societal perspective is recommended as the

appropriate reference case. All values will be adjusted for inflation. Since no follow-up measurements will be taken beyond 12 months following baseline, discounting for time preference will not be required. Given the differences in mechanisms to generate data, separate multivariable generalized-linear models (GLMs) will be estimated to predict the mean value of each resource category at each time point. GLMs permit us to choose the most appropriate mean and variance functions according to fit with the data. A multivariable GLM will also be used to predict health-related quality of life preference weights for each participant at each time point. QALYs gained by the intervention will then be estimated by using the area under the curve. The method of recycled predictions will be used to obtain the final predicted mean values for each study group and resource, which will then be summed and tested according to the relevant perspective. To account for sampling uncertainty in point estimates, both the p-values and standard errors, as well as the confidence intervals for the ICER, will be estimated by using nonparametric bootstrapping techniques within the multivariable framework. Parametric methods based on parameters obtained from bootstrapping will be used to estimate acceptability curves, which illustrate the probability that the intervention is a good value for different willingness-to-pay thresholds (e.g., cost-per-QALY). Sensitivity analyses will be performed to account for uncertain precision in assumptions and parameter estimates applied in the analysis.

**[Aim 4.]** We will examine whether the ANA moderators (executive functioning, negative emotionality, alcohol-related incentive salience) interact with CM, and if so, with which CM condition. This will help us determine whether a given moderator significantly modified the impact of CM on alcohol abstinence. First, we will create an interaction term of CM condition by the moderator in question and examine whether the interaction is significant. Second, if the interaction is significant, we will examine whether the outcome varies within each CM condition across 3 categories of the moderator in question: 1) Mean  $\pm 1$  standard deviation, 2)  $> 1$  standard deviation, and 3)  $< 1$  standard deviation. This will be accomplished by conducting a planned linear trend analysis or simple effects analysis for each CM condition, since we hypothesize that, for example, more executive dysfunction will produce worse treatment outcomes. Although we anticipate that this association will hold true for each condition, we also hypothesize that the effect will be more pronounced in the Usual CM condition. If appropriate for a clearer clinical interpretation, we will use centering (i.e., subtracting the mean from all participant values on the measure) on the moderator being examined, which is consistent with current expert recommendations.

**Missing Data.** We have developed extensive tracking procedures to reduce missing data, which will be handled in a manner consistent with current expert recommendations. We will use maximum likelihood or multiple imputation and extensive sensitivity analyses, including “missing not at random” approaches, to examine the robustness of treatment effects under varying assumptions. These approaches are preferable to other data imputation approaches, such as mean imputation.

**4.G.3 Power Analysis. [Aims 1 and 2.]** Our choice of sample size for randomization (n=240) is based on statistical power calculations for the primary aim of reducing alcohol use and the secondary aim of improving other outcomes during the final 3 months of the intervention and the 6-month follow-up period. We estimated power by using **clinically significant** cutoff estimates in conjunction with previously reported effect sizes of adapted CM interventions. Clinically significant cutoffs derive from studies of addiction treatment clinicians, who report that a 10-12% difference in dichotomous outcomes (such as percent abstinent), or a 50% decline compared to the base rate, or a doubling of continuous measures such as number of weeks abstinent, would be enough to justify adoption of a given treatment in their practice. This measure of clinical significance for continuous outcomes represents a large effect size. If used exclusively to guide our power analyses, this threshold would leave the current trial powered only on a doubling of continuous measures, which could lead to overlooking potentially meaningful effects. Thus, we powered our analysis primarily on clinically meaningful differences in binary outcomes. This approach gives us adequate power to detect clinically meaningful improvements in continuous outcomes that are less than double the continuous measures.

**Background.** In one sample of difficult-to-treat cocaine users, the lowest effect observed was a 10% increase in the proportion of negative urine samples submitted by **high-magnitude CM** participants compared to those in usual CM. In a similar sample of cocaine users, a difference of 32% was found between usual versus high-magnitude CM groups. In a sample of difficult-to-treat methadone maintained cocaine users, abstinence increased by 14% in high-magnitude CM. Thus high-magnitude CM has been shown to consistently produce clinically meaningful and statistically significant results among patients who smoke or use illicit drugs.

Although **shaping CM** is less studied, a trial with hard-to-treat smokers found a 17% increase in smoking-negative samples submitted by shaping CM participants relative to usual CM participants. Shaping CM participants also submitted an average of 21 smoking-negative samples, while usual CM participants submitted an average of 3.5 smoking-negative samples. These differences meet the above criteria for clinical significance.

With regard to our **Aim 2** outcomes, we highlight findings from a study with cocaine users identified as non-responders to usual CM. When participants received high-magnitude CM, opiate abstinence increased by 14%

and benzodiazepine abstinence increased by 11% relative to when participants received usual CM. In another study of CM for cocaine use in methadone patients, opiate abstinence increased by 8% in participants receiving high-magnitude CM. Finally, a study utilized data from a large national schizophrenia treatment trial to establish a threshold for statistical significance in PANSS outcomes (our psychiatric severity measure). They found that a change in PANSS score of 34% was considered a clinically significant difference. While this is lower than the cutoff for clinical significance noted above (i.e., 50% decline), our power analyses demonstrate that the proposed trial will be able to detect such an effect size, as well as slightly smaller differences.

